2.9.4 Other analysis

Concomitant medications will be coded using the World Health Organization Drug Dictionary (WHODrug). Concomitant medications, including those for study eye and fellow eye, will be grouped into those taken pre-randomization and those taken post-randomization as well as those taken post-treatment, based upon the starting dates of the concomitant medication and the treatment.

Number and percent of subjects in the safety population who take pre-randomization concomitant medications will be reported. Number and percent of subjects in the safety population who take post-randomization concomitant medications will be reported by treatment and by study eye vs. fellow eye. Number and percent of subjects in the safety population who take post-treatment concomitant medications will be reported by treatment and by study eye vs. fellow eye.

3 STUDY POPULATION

3.1 Definition of Subject Populations

All subjects who have the randomization procedure completed at Day 1 are considered study participants or Randomized Population as defined in the study protocol. The following subject populations are defined to assess the safety of AG-920 in comparison with placebo.

Safety Population

The safety population is defined as all subjects were randomized and who have received at least one drop of the dose (2 drops) of the study medication. The safety population will be utilized as primary population for comparative safety analyses among treatment groups.

Intention-to-treat (ITT) Population

This population is defined as all subjects who are randomized to treatment and have received at least one dose (two drops) of the study medication. Treatment identification is defined in the ITT population by treatment assignment. The ITT population will be identified and finalized before the database is locked and the study is unmasked.

The ITT population is the secondary population for safety evaluation in this study if the ITT population is not identical to the safety population.

Specular Microscopy (SM) Population

The SM population includes those subjects who are randomized and treated and have had the specular microscopy findings for at least one visit.

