9.3 Analysis populations

For this safety study, there is no Per-protocol (PP) population. Three other explicit populations are listed here, although they may be effectively synonymous in this single dose safety study.

Randomized Population: The randomized population will include all subjects who were randomized to treatment. Baseline (screening) variables and demographic characteristics will be summarized for this population.

Intent-to-Treat Population (ITT): The ITT population will include all randomized subjects who have received at least one dose (2 drops) of study medication. The ITT population will include subjects as randomized.

Safety Population: The safety population will include all randomized subjects who have received at least one dose (2 drops) of study medication. This population will be used to summarize the safety variables and will summarize subjects as treated.

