3.2 Screening and Enrollment

A screening summary including the number of subjects screened for study participation will be presented by site (Table 1.1.1).

An enrollment summary including the number of subjects enrolled, randomized, and completed the study will be presented for all enrolled subjects and by site (Table 1.1.2). Enrolled subjects include those individuals who are screened and randomized into the study. The number of subjects treated with at least one drop of the dose (2 drops) of the study medication (i.e., the safety population) will be summarized for each treatment group and overall (Table 1.1.3). The number of subjects treated with at least one dose (2 drops) of the study medication (i.e., the ITT population) will be summarized for each treatment group and overall (Table 1.1.4). The subset population of subjects tested for specular microscopy (i.e., the SM population) will be summarized for each treatment group and overall (Table 1.1.5).

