3.6 Disposition of Study Participants

Subject disposition including completion and discontinuation along with CRF-based termination reason will be summarized for safety and ITT populations (Tables 1.4.1 to 1.4.2). Subjects' early termination details will be listed for all subjects enrolled (Listing 2).

Subjects' randomized treatment, randomization (or kit) number, and randomization date as well as actual treatment received will be listed for all subjects randomized (Listing 3).

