5.2 Early Termination

Early termination will be categorically summarized for the safety population in Table 1.4.1, and for the ITT population in Table 1.4.2. Subjects' study termination details will be listed (Listing 2).

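### The set called ITT requires both drops, so the secondary safety population and Table 1.4.2 leave out one-drop subjects, and neither disposition table covers everyone randomized

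*SAP*

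**What the plan says.** The two documents give the same ITT rule. SAP 3.1 has "all subjects who are randomized to treatment and have received at least one dose (two drops) of the study medication"; protocol 9.3 has "The ITT population will include all randomized subjects who have received at least one dose (2 drops) of study medication". Both group these subjects by assigned treatment.

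The SAP's Safety Population is wider. It takes randomized subjects who have "received at least one drop of the dose (2 drops) of the study medication", and it comes first: "The safety population will be utilized as primary population for comparative safety analyses among treatment groups".

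The two-drop set has two uses beyond counts, demography and baseline tables:

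- **Secondary safety population.** SAP 3.1 states: "The ITT population is the secondary population for safety evaluation in this study". This applies only if the set is not identical to the Safety Population.
- **Disposition and early termination.** SAP 3.6 and 5.2 report these on the Safety Population in Table 1.4.1, "and for the ITT population in Table 1.4.2".

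The SAP allows for incomplete dosing. Exposure is tabulated as one or two drops (SAP 2.9.3 and 5.1), and subjects who were dosed but did not receive both drops go into Listing 4 (SAP 3.7). Protocol 9.3 expects the populations to be practically the same in a single-dose study.

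**The concern.** Receiving the second drop happens after randomization and may depend on the reaction to the first. Protocol 1.2 lists eye pain and stinging or burning at instillation among the expected AG-920 effects, and the drops are 30 seconds apart. A set that requires both drops is therefore a dose-completer set, although it carries the ITT label and is grouped as randomized. A reader would normally take a table with that label as the unselected comparison.

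The condition attached to the secondary analysis adds to the difficulty. If memberships differ, they do so because someone received only one drop, so the analysis is called for by the same subjects it leaves out. If some of them stopped because they did not tolerate instillation, and more of them are on AG-920 than on vehicle, the secondary view looks more favourable to AG-920 than the Safety Population does.

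A second gap concerns subjects who were randomized but never dosed. Both disposition tables start from dosed subjects, so neither accounts for everyone randomized.

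**Working it through.** **Who is in each set under the SAP**

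| Drops received | Randomized | Safety (SAP) | ITT | Table 1.4.1 | Table 1.4.2 |
|---|---|---|---|---|---|
| 0 | yes | no | no | no | no |
| 1 | yes | yes | no | yes | no |
| 2 | yes | yes | yes | yes | yes |

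Safety and ITT differ in membership only in the one-drop row. A dosing error could move a subject between arms, but not in or out of either set. The zero-drop row is outside both disposition tables.

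**Size of the effect on Table 1.4.2**

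The documents give no rate for one-drop dosing or early termination, so there is no planned figure to reproduce. Inputs for the AG-920 arm:

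- N = 160 planned AG-920 subjects (SAP 2.5; 240 × 2/3 = 160).
- b = 2 early terminations among two-drop subjects (assumed).
- k = subjects who stop after one drop and also leave the study (assumed, 0 to 8).

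Safety rate = (b + k)/N. ITT rate = b/(N − k). The difference simplifies to (k/N) × [1 − b/(N − k)].

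| k | Safety (Table 1.4.1) | ITT (Table 1.4.2) | Difference, points |
|---|---|---|---|
| 0 | 2/160 = 1.25% | 2/160 = 1.25% | 0 |
| 1 | 3/160 = 1.875% | 2/159 = 1.26% | 0.62 |
| 3 | 5/160 = 3.125% | 2/157 = 1.27% | 1.85 |
| 5 | 7/160 = 4.375% | 2/155 = 1.29% | 3.08 |
| 8 | 10/160 = 6.25% | 2/152 = 1.32% | 4.93 |

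Each such subject costs about 0.6 points. Changing b hardly matters: at k = 3 the difference is 1.88 points with b = 0 and 1.83 with b = 4.

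**Never-dosed subjects**

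Let m randomized AG-920 subjects receive no drops, with b = 2 and k = 0. Safety and ITT then give the same rate, 2/(160 − m). For m = 2 this is 2/158 = 1.27%, against 4/160 = 2.50% of all randomized. For m = 5 it is 2/155 = 1.29%, against 7/160 = 4.375%. There is no gap between the two populations; both are incomplete as an account of disposition.

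**Outputs tied to the two-drop set**

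The SAP's table list names ITT for Tables 1.1.4 (count), 1.2.3 (demography), 1.3.2 (baseline eye characteristics) and 1.4.2 (disposition). No adverse-event, BCVA, IOP or slit-lamp table is named for ITT, so the secondary safety evaluation promised in SAP 3.1 has no listed output for those measures.

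**The case against.** The strongest reply is that little is hidden. The SAP's primary safety comparisons keep one-drop subjects, and so does Table 1.4.1. Table 3.1.1 shows one against two drops by treatment, and Tables 1.1.3 and 1.1.4 show both population counts by arm. Table 4.1.1 summarizes adverse events for all randomized subjects. Listings 2 to 4 show early terminations, assigned and actual treatment, and incomplete dosing. Table 1.1.4 is itself titled as a complete-treatment summary. All of this stands and limits the reach of the point.

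The reply also says that one-drop subjects may be rare or absent. Clinic staff give both drops, protocol 1.2 describes the expected effects as temporary and mild, and providing a one-drop category does not predict that anyone will fall into it. That stands too, and is why k is only an assumption.

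Missing the second drop is, in addition, not early termination. Protocol 3.6.1 defines completion by visits and the phone call, and 3.6.2 still seeks later safety assessments after treatment stops. Table 1.4.2 is therefore affected only by one-drop subjects who also leave.

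Finally, Table 1.1.2 covers all enrolled subjects as well as each site. The SAP text does not say whether it splits by arm or gives reasons, and the shells are not in the available text. The firm statement is limited to Tables 1.4.1 and 1.4.2.

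None of this justifies making a dose-completer set the secondary safety population. If everyone receives two drops, correcting the rule changes no tolerability result; if not, the rule removes the subjects of most interest.

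**Conclusion.** The point holds as a flaw in a secondary analysis set and in the denominator of the disposition tables. Any bias is toward tolerability, is confined to the two-drop set and Table 1.4.2, and is zero when nobody stops after one drop. Its illustrative size is about 0.6 percentage points per one-drop AG-920 subject who also leaves the study, given 160 in the arm and an assumed 2 other early terminations.

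Three stronger readings might be inferred, and the documents do not support them:

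- **That the main safety conclusions, or the primary endpoint of withdrawals due to TEAEs, are biased.** Under the SAP these rest on the at-least-one-drop population. This does depend on the SAP definition governing: protocol 9.3 requires two drops for its Safety Population as well, and the two texts need to be reconciled.
- **That never-dosed subjects bias tolerability.** They have no exposure, carry no tolerability information and are outside the Safety Population too. They bear only on the completeness of disposition.
- **That adverse-event incidence will be understated in an ITT table.** No such table is listed.

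**What to change.** - In SAP 3.1 and protocol 9.3, either define ITT as all randomized subjects by assigned treatment, or drop the label. The first option makes it the same set as the existing Randomized Population, so dropping the label is equally clean.
- Base Table 1.4.2 on all randomized subjects by assigned arm, with reasons for leaving.
- Remove the two-drop set as a secondary safety population. If it is still wanted, name it for what it is: subjects receiving two drops.
- Keep safety comparisons on the at-least-one-drop Safety Population.

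The cost is a reworded definition in two documents and a changed denominator in one disposition table. Table 1.4.2 may show a few more non-completers, and the ITT demography table becomes redundant with the Randomized one.

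One item needs confirming. Listings 2 and 3 are planned for all enrolled or randomized subjects, but protocol 10.3 and 10.4 commit to EDC recording for subjects who consent and are dosed. The sponsor should check that arm and exit reason are captured for anyone randomized and not dosed.

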3.2 Screening and Enrollment

A screening summary including the number of subjects screened for study participation will be presented by site (Table 1.1.1).

An enrollment summary including the number of subjects enrolled, randomized, and completed the study will be presented for all enrolled subjects and by site (Table 1.1.2). Enrolled subjects include those individuals who are screened and randomized into the study. The number of subjects treated with at least one drop of the dose (2 drops) of the study medication (i.e., the safety population) will be summarized for each treatment group and overall (Table 1.1.3). The number of subjects treated with at least one dose (2 drops) of the study medication (i.e., the ITT population) will be summarized for each treatment group and overall (Table 1.1.4). The subset population of subjects tested for specular microscopy (i.e., the SM population) will be summarized for each treatment group and overall (Table 1.1.5).

3.3 Population Demography

For subjects enrolled/randomized, safety, ITT, and SM populations, descriptive summaries of demography and baseline characteristics will be presented for each subject group and overall to establish baseline comparability (Tables 1.2.1 to 1.2.4).

Demography includes calculated age in years (continuous and categorical 18 to 29, 30 to 39, 40 to 49, 50 to 64, and 65+), gender, race, and ethnicity. Demography will also be listed for all subjects enrolled (Listing 1). Since this study collected only subject's birth year, rather than birth date, subject's age will be calculated as informed consent year minus birth year.

3.4 Disease Characteristics and Prior Treatment

For the safety, ITT and SM populations, descriptive summaries of baseline study eye characteristics will be presented for each treatment group and overall to establish baseline comparability (Tables 1.3.1 to 1.3.3).

BCVA and other characteristics of the study and fellow eye will be listed for all subjects enrolled (Listing 1).

3.5 Medical History

Medical history will be listed in listing (Listing 10) and CRF data tabulation. Medical history will be coded using the Medical Dictionary for Regulatory Activities (MedDRA).

3.6 Disposition of Study Participants

Subject disposition including completion and discontinuation along with CRF-based termination reason will be summarized for safety and ITT populations (Tables 1.4.1 to 1.4.2). Subjects' early termination details will be listed for all subjects enrolled (Listing 2).

Subjects' randomized treatment, randomization (or kit) number, and randomization date as well as actual treatment received will be listed for all subjects randomized (Listing 3).

3.7 Protocol Deviations and Violations

A summary of protocol deviation and violations will be provided for safety population (Table 1.5.1). Subjects who are randomized to receive double-masked treatment in the study and included in the safety population, but do not have two drops of the dose will be listed for subjects randomized (Listing 4).

4 EFFICACY EVALUATION

Not applicable.

5 SAFETY EVALUATION

For safety evaluation, the safety population as defined in Section 3.1 will be utilized to conduct safety analyses among treatment groups. Subjects included in the safety population will be listed in Listing 5.

5.1 Extent of Drug Exposure

Exposure to study medication will be tabulated by treatment in Table 3.1.1 for number of drops received, using the following categories: 1 drop and 2 drops. The tabulations will be done for the safety population, and for man and woman, separately.

Individual subjects' treatment exposure (drops) will be listed by treatment for the safety population (Listing 3).

5.2 Early Termination

Early termination will be categorically summarized for the safety population in Table 1.4.1, and for the ITT population in Table 1.4.2. Subjects' study termination details will be listed (Listing 2).

5.3 Adverse Events

An overall summary of AEs reported in this study will be provided in Table 4.1.1 for study participants and in Table 4.1.2 for the safety population. The incidences of subjects reporting pre-treatment AE will be reported in Table 4.2.1 for the pre-randomization period and in Table 4.2.2 for the treatment-emergent AEs by treatment. Those treatment-emergent AE by preferred terminology that are reported by more than 5% of subjects in any individual treatment group will be tabulated in Table 4.2.3.

Incidences of subjects reporting treatment-emergent AEs (TEAEs) will also be tabulated by treatment for the TEAEs associated with the study eye in Table 4.2.5 and for the TEAEs associated with fellow eye in Table 4.2.6.

Incidences of subjects reporting treatment-emergent AEs will also be tabulated by onset time (on-treatment day vs. off-treatment day) in Table 4.3.1 for all TEAEs, and in Table 4.3.2 for the TEAEs associated with the study eye, and in Table 4.3.3 for the TEAEs associated with the fellow eye.

The severity of the treatment-emergent AEs and the relationship to the investigational product will be summarized in Table 4.4.1.

Treatment-emergent AEs associated with early terminations and serious AEs will be summarized by preferred term, respectively, in Table 4.4.2 and Table 4.4.3 for all TEAEs, in Table 4.4.4 and Table 4.4.5 for the TEAEs associated with the study eye, and in Table 4.4.6 and 4.4.7 for the TEAEs associated with the fellow eye.

Details of AEs associated with both study and fellow eyes will be listed for each subject (Listing 6)

Details of AEs associated with early terminations will be listed for each subject (Listing 7). SAEs, including deaths, will be listed (Listing 8).

Narratives will be presented for all deaths, non-fatal serious adverse events, and subjects withdrawn due to adverse events.

Female pregnancy results will be listed (Listing 9).

5.4 Best Corrected Visual Acuity

Visual Acuity data will be summarized at each time point using both continuous summaries (Logarithmic Minimum Angle of Resolution, logMAR), including change from baseline, and discrete summaries, including change from baseline in the number of lines and the proportion of subjects with a worsening of ≥ 3 lines from baseline.

Descriptive and inferential statistics of BCVA in logMAR will be presented by treatment for the pre-dose (screening) and post-dose assessments and changes in post-dose assessment from pre-dose in Table 5.1.1 for the study eye and in Table 5.1.2 for the fellow eye.

5.5 Intraocular Pressure

Descriptive and inferential statistics of IOP will be presented by treatment for the pre-dose (screening) and post-dose assessments and changes in post-dose assessment from pre-dose in Table 5.2.1 for the study eye and in Table 5.2.2 for the fellow eye.

5.6 Biomicroscopy and External Eye Exam

Descriptive and inferential statistics of biomicroscopy (Slit-Lamp) total severity score will be presented by treatment for the pre-dose (screening) and post-dose assessments and their changes in post-dose assessment from pre-dose in Table 6.1.1 for the study eye and in Table 6.1.2 for the fellow eye.

5.7 Specular Microscopy

Mean and mean changes in data from the reading center from specular microscopy at baseline and 90 days post dosing from screening will be reported by treatment groups in Table 6.2.1 for the study eye and in Table 6.2.2 for the fellow eye.

5.8 Concomitant Medication

Number and percent of subjects who take pre-randomization concomitant medications will be reported in Table 7.1.1. Number and percent of subjects who take pre-randomization concomitant medications will be reported by treatment in Table 7.1.2. Number and percent of subjects who take post-treatment concomitant medications will be reported by treatment in Table 7.1.3.

Number and percent of subjects who take pre-randomization concomitant medications for eye treatment will be reported in Table 7.2.1 for study eye and in Table 7.2.2 for the fellow eye.

Number and percent of subjects who take post-randomization concomitant medications for eye treatment will be reported in Table 7.3.1 for study eye and in Table 7.3.2 for the fellow eye.

6 REFERENCES

Study Protocol No. AG920-CS303 version 1.0.

7 List of Statistical Table Shells

Statistical table shells are provided after the text portion. Table shells are presented only for those tables with a unique format. Tables with duplicate formats are indicated in the list of tables below. Final TFL sets will be numbered with the ICH E3 title as listed below.

Table Title (SAP)	ICH E3 Title for Section 14 (TFL)
Table 1.1.1 Screening Summary	Table 14.1.1.1
Table 1.1.2 Enrollment Summary: Randomized population	Table 14.1.1.2
Table 1.1.3 Randomized Treatment Summary: Safety population	Table 14.1.1.3
Table 1.1.4 Randomized Complete Treatment Summary: ITT population	Table 14.1.1.4
Table 1.1.5 Specular Microscopy (SM) Summary: SM population	Table 14.1.1.5
Table 1.2.1 Demography: Randomized population	Table 14.1.2.1.1
Table 1.2.2 Demography: Safety population	Table 14.1.2.1.2
Table 1.2.3 Demography: ITT population	Table 14.1.2.1.3
Table 1.2.4 Demography: SM population	Table 14.1.2.1.4
Table 1.3.1 Baseline Eye Characteristics: Safety population	Table 14.1.2.2.1
Table 1.3.2 Baseline Eye Characteristics: ITT population	Table 14.1.2.2.2
Table 1.3.3 Baseline Eye Characteristics: SM population	Table 14.1.2.2.3
Table 1.4.1 Disposition: Safety population	Table 14.1.3.1
Table 1.4.2 Disposition: ITT population	Table 14.1.3.2
Table 1.5.1 Protocol Deviations: Safety population	Table 14.1.6.1
Table 3.1.1 Treatment Exposure of All Applications (including active and placebo): Safety population	Table 14.1.3.3
Table 4.1.1 Overall Summary of Adverse Events: Randomized population	Table 14.3.1.1
Table 4.1.2 Overall Summary of Adverse Events: Safety population	Table 14.3.1.2
Table 4.2.1 Incidence of Pre-Treatment AEs by Preferred Terminology	Table 14.3.1.3
Table 4.2.2 Incidence of Treatment-Emergent AEs by Preferred Terminology	Table 14.3.1.4
Table 4.2.3 Treatment-Emergent AEs with >5% Subjects Reporting by Preferred Terminology	Table 14.3.1.5
Table 4.2.4 Incidence of Subjects Reporting Post-Treatment AEs by Preferred Terminology	Table 14.3.1.6
Table 4.2.5 Incidence of Subjects Reporting Study-Eye Treatment-Emergent AEs by Preferred terminology	Table 14.3.1.7
Table 4.2.6 Incidence of Subjects Reporting Fellow Eye Treatment-Emergent AEs by Preferred terminology	Table 14.3.1.8
Table 4.3.1 Incidence of Treatment-Emergent AEs and Onset Time	Table 14.3.1.9
Table 4.3.2 Incidence of Study Eye Treatment-Emergent AEs and Onset Time	Table 14.3.1.10
Table 4.3.3 Incidence of Fellow Eye Treatment-Emergent AEs and Onset Time	Table 14.3.1.11
Table 4.4.1 Treatment-Emergent AEs by Severity and Relationship to Study Treatment	Table 14.3.1.12
Table 4.4.2 Incidence of Treatment-Emergent AEs Associated with Discontinuations by Preferred Terminology	Table 14.3.2.3.1
Table 4.4.3 Incidence of Treatment-Emergent SAEs by Preferred Terminology	Table 14.3.2.2.1

Table Title (SAP)	ICH E3 Title for Section 14 (TFL)
Table 4.4.4 Incidence of Study-Eye Treatment-Emergent AEs Associated with Discontinuations and by Preferred Terminology	Table 14.3.2.3.2
Table 4.4.5 Incidence of Study-Eye Treatment-Emergent SAEs by Preferred Terminology	Table 14.3.2.2.2
Table 4.4.6 Incidence of Fellow-Eye Treatment-Emergent AEs Associated with Discontinuations and by Preferred Terminology	Table 14.3.2.3.3
Table 4.4.7 Incidence of Fellow-Eye Treatment-Emergent SAEs by Preferred Terminology	Table 14.3.2.2.3
Table 5.1.1 Summary and Analysis of BCVA Scores: Study Eye	Table 14.3.4.1
Table 5.1.2 Summary and Analysis of BCVA Scores: Fellow Eye	Table 14.3.4.2
Table 5.2.1 Summary and Analysis of IOP Measures: Study Eye	Table 14.3.4.3
Table 5.2.2 Summary and Analysis of IOP Measures: Fellow Eye	Table 14.3.4.4
Table 6.1.1 Summary and Analysis of Biomicroscopy (slit lamp) Severity Scores: Study Eye	Table 14.3.5.1
Table 6.1.2 Summary and Analysis of Biomicroscopy (slit lamp) Severity Scores: Fellow Eye	Table 14.3.5.2
Table 6.2.1 Summary of Specular Microscopy Test: Study Eye	Table 14.3.5.3
Table 6.2.2 Summary of Specular Microscopy Test: Fellow Eye	Table 14.3.5.4
Table 7.1.1 Summary of Pre-Randomization Concomitant Medication Use: Safety population	Table 14.1.5.1
Table 7.1.2 Summary of Post-Randomization Concomitant Medication Use: Safety population	Table 14.1.5.2
Table 7.1.3 Summary of Post-Treatment Concomitant Medication Use: Safety population	Table 14.1.5.3
Table 7.2.1 Summary of Pre-Randomization Study-Eye Concomitant Medication Use: Safety population	Table 14.1.5.4
Table 7.2.2 Summary of Pre-Randomization Fellow-Eye Concomitant Medication Use: Safety population	Table 14.1.5.5
Table 7.3.1 Summary of Post-Randomization Study-Eye Concomitant Medication Use: Safety population	Table 14.1.5.6
Table 7.3.2 Summary of Post-Randomization Fellow-Eye Concomitant Medication Use: Safety population	Table 14.1.5.7

8 List of Key Listing Shells

